7.2.2 Reporting of Pregnancy and Lactation to the Sponsor and to Merck

Although pregnancy and lactation are not considered adverse events, it is the responsibility of investigators or their designees to report any pregnancy or lactation in a subject (spontaneously reported to them), including the pregnancy of a male subject's female partner that occurs during the trial or within 120 days of completing the trial completing the trial, or 30 days following cessation of treatment if the subject initiates new anticancer therapy, whichever is earlier. All subjects and female partners of male subjects who become pregnant must be followed to the completion/termination of the pregnancy. Pregnancy outcomes of spontaneous abortion, missed abortion, benign hydatidiform mole, blighted ovum, fetal death, intrauterine death, miscarriage and stillbirth must be reported as serious events (Important Medical Events). If the pregnancy continues to term, the outcome (health of infant) must also be reported.

Such events must be reported within 24 hours to the Sponsor and within 2 working days to Merck Global Safety. (Attn: Worldwide Product Safety; [contact])

7.2.3 Immediate Reporting of Adverse Events to the Sponsor and to Merck

7.2.3.1 Serious Adverse Events

A serious adverse event is any adverse event occurring at any dose or during any use of Merck's product that:

- Results in death;
- Is life threatening;
- Results in persistent or significant disability/incapacity;
- Results in or prolongs an existing inpatient hospitalization;
- Is a congenital anomaly/birth defect;
- Is a new cancer (that is not a condition of the study);
- Is associated with an overdose;
- Is another important medical event
- Overdose

Refer to Table 10 for additional details regarding each of the above criteria.

Progression of the cancer under study is not considered an adverse event unless it results in hospitalization or death.

Any serious adverse event, or follow up to a serious adverse event, including death due to any cause other than progression of the cancer under study that occurs to any subject from the time the consent is signed through 90 days following cessation of treatment, or the initiation of new anti-cancer therapy, whichever is earlier, whether or not related to Merck product, must be reported within 24 hours to the Sponsor and within 2 working days to Merck Global Safety.

Non-serious Events of Clinical Interest will be forwarded to Merck Global Safety and will be handled in the same manner as SAEs.

Additionally, any serious adverse event, considered by an investigator who is a qualified physician to be related to Merck product that is brought to the attention of the investigator at any time outside of the time period specified in the previous paragraph also must be reported immediately to the Sponsor and to Merck.

SAE reports and any other relevant safety information are to be forwarded to the Merck Global Safety [contact]

A copy of all 15 Day Reports and Annual Progress Reports is submitted as required by FDA, European Union (EU), Pharmaceutical and Medical Devices agency (PMDA) or other local regulators. Investigators will cross reference this submission according to local regulations to the Merck Investigational Compound Number (IND, CSA, etc.) at the time of submission.

Additionally investigators will submit a copy of these reports to Merck & Co., Inc. (Attn: Worldwide Product Safety; [contact]) at the time of submission to FDA.

All subjects with serious adverse events must be followed up for outcome.

7.2.3.2 Events of Clinical Interest

Selected non-serious and serious adverse events are also known as Events of Clinical Interest (ECI) and must be recorded as such on the Adverse Event case report forms/worksheets and reported within 24 hours to the Sponsor and within 2 working days to Merck Global Safety. (Attn: Worldwide Product Safety; [contact])

Events of clinical interest for this trial include:

1. an overdose of Merck product, as defined in Section 7.2.1 - Definition of an Overdose for This Protocol and Reporting of Overdose to the Sponsor, that is not associated with clinical symptoms or abnormal laboratory results.

2. an elevated AST or ALT lab value that is greater than or equal to 3X the upper limit of normal and an elevated total bilirubin lab value that is greater than or equal to 2X the upper limit of normal and, at the same time, an alkaline phosphatase lab value that is less than 2X the upper limit of normal, as determined by way of protocol-specified laboratory testing or unscheduled laboratory testing.*

*Note: These criteria are based upon available regulatory guidance documents. The purpose of the criteria is to specify a threshold of abnormal hepatic tests that may require an additional evaluation for an underlying etiology. The trial site guidance for assessment and follow up of these criteria can be found in the Investigator Trial File Binder (or equivalent).

3. In the event a subject develops any of the following AEs, a detailed narrative of the event should be reported as an ECI to the Sponsor within 24 hours and to Merck Global Safety within 2 working days of the event:

- a. Grade \geq 3 diarrhea
- b. Grade \geq 3 colitis
- c. Grade ≥ 2 pneumonitis
- d. Grade \geq 3 hypo- or hyperthyroidism

A separate guidance document has been provided entitled "event of Clinical Interest and Immune-Related Adverse Event Guidance Document." This document provides guidance regarding identification, evaluation and management of ECIs and irAEs. Additional ECIs are identified in this guidance document and also need to be reported to the Sponsor within 24 hours and to Merck Global Safety within 2 working days of the event.

Subjects should be assessed for possible ECIs prior to each dose. Lab results should be evaluated and subjects should be asked for signs and symptoms suggestive of an immune-

related event. Subjects who develop an ECI thought to be immune-related should have additional testing to rule out other etiologic causes. If lab results or symptoms indicate a possible immune-related ECI, then additional testing should be performed to rule out other etiologic causes. If no other cause is found, then it is assumed to be immune-related.

ECIs that occur in any subject from the date of first dose through 90 days following cessation of treatment, or the initiation of a new anticancer therapy, whichever is earlier, whether or not related to the Merck's product, must be reported within 24 hours to the Sponsor and to Merck Global Safety within 2 working days.

7.2.4 Evaluating Adverse Events

An investigator who is a qualified physician will evaluate all adverse events according to the NCI Common Terminology for Adverse Events (CTCAE), version 4.0. Any adverse event which changes CTCAE grade over the course of a given episode will have each change of grade recorded on the adverse event case report forms/worksheets.

All adverse events regardless of CTCAE grade must also be evaluated for seriousness.

Product: MK-3475 **Protocol/Amendment No.:**

Table 10 Evaluating Adverse Events

An investigator, who is a qualified physician, will evaluate all adverse events as to:

V4.0 CTCAE Grading	Grade 1	Mild; asymptomatic or mid symptoms; clinical or diagnostic observations only; intervention not indicated.						
	Grade 2	Moderate; minimal, local or noninvasive intervention indicated; limiting age-appropriate instrumental ADL.						
	Grade 3	Severe or medically significant but not immediately life-threatening; hospitalization or prolongation or hospitalization indicated;						
		disabling; limiting self-care ADL.						
	Grade 4	Life threatening consequences; urgent intervention indicated.						
	Grade 5	Death related to AE						
Seriousness	A serious adverse	event is any adverse event occurring at any dose or during any use of Merck product that:						
	†Results in death							
	†Is life threatenin	ng; or places the subject, in the view of the investigator, at immediate risk of death from the event as it occurred (Note: This does not include an						
	adverse event that	, had it occurred in a more severe form, might have caused death.); or						
	†Results in a pers	sistent or significant disability/incapacity (substantial disruption of one's ability to conduct normal life functions); or						
	†Results in or prolongs an existing inpatient hospitalization (hospitalization is defined as an inpatient admission, regardless of length of stay, even if the hospitalization is a precautionary measure for continued observation. (Note: Hospitalization [including hospitalization for an elective procedure] for a preexisting condition which has not worsened does not constitute a serious adverse event.); or							
	†Is a congenital anomaly/birth defect (in offspring of subject taking the product regardless of time to diagnosis);or							
	Is a new cancer: (that is not a condition of the study) or							
	Is an overdose (whether accidental or intentional). Any adverse event associated with an overdose is considered a serious adverse event. An overdose that is not							
	associated with an adverse event is considered a non-serious event of clinical interest and must be reported within 24 hours.							
	Other important medical events that may not result in death, not be life threatening, or not require hospitalization may be considered a serious adverse event when,							
	based upon appropriate medical judgment, the event may jeopardize the subject and may require medical or surgical intervention to prevent one of the outcomes							
	listed previously (designated above by a [†]).							
Duration		ind stop dates of the adverse event. If less than 1 day, indicate the appropriate length of time and units						
Action taken		vent cause the Merck product to be discontinued?						
Relationship to	Did the Merck product cause the adverse event? The determination of the likelihood that the Merck product caused the adverse event will be provided by an							
test drug		s a qualified physician. The investigator's signed/dated initials on the source document or worksheet that supports the causality noted on the AE						
U	form, ensures that a medically qualified assessment of causality was done. This initialed document must be retained for the required regulatory time frame. The							
	criteria below are intended as reference guidelines to assist the investigator in assessing the likelihood of a relationship between the test drug and the adverse event							
	based upon the available information.							
	The following components are to be used to assess the relationship between the Merck product and the AE; the greater the correlation with the components and							
	their respective elements (in number and/or intensity), the more likely the Merck product caused the adverse event (AE):							
	Exposure	Is there evidence that the subject was actually exposed to the Merck product such as: reliable history, acceptable compliance assessment (pill count, diary, etc.), expected pharmacologic effect, or measurement of drug/metabolite in bodily specimen?						
	Time Course	Did the AE follow in a reasonable temporal sequence from administration of the Merck product?						
		Is the time of onset of the AE compatible with a drug-induced effect (applies to trials with investigational medicinal product)?						
	Likely Cause	Is the AE not reasonably explained by another etiology such as underlying disease, other drug(s)/vaccine(s), or other host or environmental factors						

Relationship	The following com	ponents are to be used to assess the relationship between the test drug and the AE: (continued)
to Merck	Dechallenge	Was the Merck product discontinued or dose/exposure/frequency reduced?
product		If yes, did the AE resolve or improve?
(continued)		If yes, this is a positive dechallenge. If no, this is a negative dechallenge.
		(Note: This criterion is not applicable if: (1) the AE resulted in death or permanent disability; (2) the AE resolved/improved despite continuation
		of the Merck product; or (3) the trial is a single-dose drug trial); or (4) Merck product(s) is/are only used one time.)
	Rechallenge	Was the subject re-exposed to the Merck product in this study?
		If yes, did the AE recur or worsen?
		If yes, this is a positive rechallenge. If no, this is a negative rechallenge.
		(Note: This criterion is not applicable if: (1) the initial AE resulted in death or permanent disability, or (2) the trial is a single-dose drug trial); or
		(3) Merck product(s) is/are used only one time).
		NOTE: IF A RECHALLENGE IS PLANNED FOR AN ADVERSE EVENT WHICH WAS SERIOUS AND WHICH MAY HAVE BEEN
		CAUSED BY THE MERCK PRODUCT, OR IF REEXPOSURE TO THE MERCK PRODUCT POSES ADDITIONAL POTENTIAL
		SIGNIFICANT RISK TO THE SUBJECT, THEN THE RECHALLENGE MUST BE APPROVED IN ADVANCE BY THE U.S. CLINICAL
	 	MONITOR AS PER DOSE MODIFICATION GUIDELINES IN THE PROTOCOL.
	Consistency	Is the clinical/pathological presentation of the AE consistent with previous knowledge regarding the Merck product or drug class pharmacology
	with Trial	or toxicology?
	Treatment	
The second of	Profile	
consideration of th		reported on the case report forms /worksheets by an investigator who is a qualified physician according to his/her best clinical judgment, including
Record one of the	e following	Use the following scale of criteria as guidance (not all criteria must be present to be indicative of a Merck product relationship).
Yes, there is a rea possibility of Mer relationship.		There is evidence of exposure to the Merck product. The temporal sequence of the AE onset relative to the administration of the Merck product is reasonable. The AE is more likely explained by the Merck product than by another cause.
No, there is not a possibility Merck relationship		Subject did not receive the Merck product OR temporal sequence of the AE onset relative to administration of the Merck product is not reasonable OR there is another obvious cause of the AE. (Also entered for a subject with overdose without an associated AE.)

7.2.5 Sponsor Responsibility for Reporting Adverse Events

All Adverse Events will be reported to regulatory authorities, IRB/IECs and investigators in accordance with all applicable global laws and regulations.

8.0 STATISTICAL ANALYSIS PLAN

8.1 Statistical Analysis Plan Summary

The first 6 patients enrolled in this study will constitute the phase I component of the clinical trial. All patients enrolled in the study will be analyzed for the safety and efficacy endpoints of the study.

This will be a single arm phase II study which will enroll 35 patients in Cohort 1 and 35 patients in Cohort 2. All patients enrolled in the study (both in the phase I run in and phase II expansion) will be analyzed for the safety and efficacy endpoints of the study. For both Cohorts, using a 1-sided 0.07 level (exact) test with a null hypothesis of 20% response rate to the MK-3475 and vorinostat combination, an alternative of 40%, and 89% power (exact), 11/35 (31%) responses would be considered evidence to rule out an RR of < 20%. With 35 patients, frequencies can be estimated to within 17% with 95% confidence.

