2.1.2. Phase II expansion

After the first 6 patients have been assessed for DLTs upon completion of cycle 1 of treatment, and the appropriate vorinostat dose and MK-3475 dosing interval determined for phase II expansion, additional patients will be enrolled with RMHNSCC (Cohort 1) and RMSCG (Cohort 2) to total 35 patients in each cohort. Patients enrolled in the phase I and II portions will be used to assess the safety and efficacy outcomes of interest in each cohort.

Patients will be evaluated every 9 weeks $(63 \pm 7 \text{ days})$ with radiographic imaging to assess response to treatment. All imaging will be assessed using Response Evaluation Criteria in Solid Tumors (RECIST) 1.1 Patients will also be assessed by immune response criteria (IrRC – Appendix) for determination of overall response rate (ORR) and progression-free survival (PFS). Adverse events will be monitored throughout the trial and graded in severity according to the guidelines outlined in the NCI Common Terminology Criteria for Adverse Events (CTCAE) version 4.0.

Treatment with MK-3475 and vorinostat will continue until two years of therapy have been administered, or until

- 1. Documented disease progression (investigators may elect to continue MK-3475 treatment beyond progression in specific circumstances, unacceptable adverse event(s)
- 2. Intercurrent illness that prevents further administration of treatment
- 3. Investigator's decision to withdraw the subject
- 4. Subject withdraws consent,
- 5. Pregnancy of the subject,
- 6. Non-compliance with trial treatment or procedure requirements, or administrative reasons.

MK-3475 and vorinostat treated subjects who attain an investigator-determined confirmed complete response (CR) per RECIST 1.1 and IrRC may consider stopping trial treatment. Patients with a CR may continue on therapy for up to 2 cycles until a confirmatory scan is undertaken. If patients upon a confirmed CR progress they may continue therapy on a second course of therapy the combination until toxicity, progression. These subjects will be eligible for re-treatment for up to one year with MK-3475 and vorinostat after they have experienced radiographic disease progression at the discretion of the investigator according to the criteria in Section 5.1.4; this re-treatment will be the Second Course Phase. Response or progression in the Second Course Phase will not count towards the ORR and PFS of the primary endpoint in this trial.

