2.2 Trial Diagram

3.0 OBJECTIVE(S) & HYPOTHESIS(ES)

3.1 Primary Objective(s) & Hypothesis(es)

Objective: Determine the safety and tolerability of MK-3475 in combination with vorinostat patients with RMHNSCC and RMSGC

Hypothesis: The combination of MK-3475 and vorinostat is safe and well tolerated in patients with RMHNSCC and RMSGC

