4.2.3 Rationale for Endpoints

Both vorinostat and MK-3475 appear to be well tolerated as a single agents and have FDA approved doses and indications. These two drugs have non-overlapping mechanisms of action. There has been no reported clinical experience with the combination of vorinostat and MK-3475. Therefore a phase I/II design, wherein a limited phase I run in cohort is initially enrolled, was felt to be most appropriate to study this combination, with safety and tolerability as the primary endpoint of interest.

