7.2 Assessing and Recording Adverse Events

An adverse event is defined as any untoward medical occurrence in a patient or clinical investigation subject administered a pharmaceutical product and which does not necessarily have to have a causal relationship with this treatment. An adverse event can therefore be any unfavorable and unintended sign (including an abnormal laboratory finding, for example), symptom, or disease temporally associated with the use of a medicinal product or protocol-specified procedure, whether or not considered related to the medicinal product or protocol-specified procedure. Any worsening (i.e., any clinically significant adverse change in frequency and/or intensity) of a preexisting condition that is temporally associated with the use of the Merck's product, is also an adverse event.

Changes resulting from normal growth and development that do not vary significantly in frequency or severity from expected levels are not to be considered adverse events. Examples of this may include, but are not limited to, teething, typical crying in infants and children and onset of menses or menopause occurring at a physiologically appropriate time.

Merck product includes any pharmaceutical product, biological product, device, diagnostic agent or protocol-specified procedure, whether investigational (including placebo or active comparator medication) or marketed, manufactured by, licensed by, provided by or distributed by Merck for human use.

Adverse events may occur during the course of the use of Merck product in clinical trials or within the follow-up period specified by the protocol, or prescribed in clinical practice, from overdose (whether accidental or intentional), from abuse and from withdrawal.

Adverse events will be recorded from the time the first dose of either vorinostat or MK-3475 is administered through 30 days following cessation of treatment and at each examination on the Adverse Event case report forms/worksheets. After 30 days, adverse events related to either MP-3475 or vorinostat will be followed until resolution or stabilization of the AE or until the beginning of a new anti-neoplastic therapy, whichever occurs first. The reporting timeframe for adverse events meeting any serious criteria is described in section 7.2.3.1.

Only adverse events that meet the following definition will be recorded.

- All grade 3 and higher adverse events

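### Define the safety set as treated rather than enrolled patients, and state a pooled same-regimen toxicity estimate beside the per-cohort one

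*Combined protocol and SAP*

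**What the plan says.** Section 4.2.3 describes the design as one "with safety and tolerability as the primary endpoint of interest". The primary objective in Section 3.1 is a single statement for both diseases: "Determine the safety and tolerability of MK-3475 in combination with vorinostat patients with RMHNSCC and RMSGC".

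Section 8.1 plans to "enroll 35 patients in Cohort 1 and 35 patients in Cohort 2". It states twice, in near-identical words, which patients are analysed: "All patients enrolled in the study will be analyzed for the safety and efficacy endpoints of the study". No separate set of treated patients is defined. The only precision statement follows the response-rate test: "With 35 patients, frequencies can be estimated to within 17% with 95% confidence". Section 8.2 summarises toxicity as counts and percentages by type, and names no denominator, pooling rule or confidence interval.

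Section 2.1.2 says that run-in and expansion patients together are "used to assess the safety and efficacy outcomes of interest in each cohort".

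On data collection, Section 7.2 says: "Adverse events will be recorded from the time the first dose of either vorinostat or MK-3475 is administered". Serious adverse events have a wider window in Section 7.2.3.1: "from the time the consent is signed through 90 days following cessation of treatment".

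Three other places bear on the point. Section 5.4 intends every enrolled patient to be given both drugs. Section 2.1.1 draws the six run-in patients from either cohort for one joint dose-limiting toxicity (DLT) decision, and moves phase II to a different schedule if more than two of them have a DLT. Section 5.9 leaves out of the DLT rate, and replaces, run-in patients who had less than 90% of the cycle 1 infusion and no DLT.

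**The concern.** There are two separate issues.

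The first is the denominator. All-enrolled is the usual conservative choice for response, because an untreated patient counts as a non-responder. For toxicity the same choice works the other way: a patient who was never exposed counts as free of toxicity. Such a patient has no general adverse event record. A serious event after consent would be reported, but Table 10 in Section 7.2.4 directs that an event in someone who did not receive the product be judged unrelated. Any error can therefore only make the combination look safer, and it falls on the primary endpoint.

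The second is the level of summary. Section 4.2.3 says there was no reported clinical experience with this combination, and Section 4.1.2 says that safety data will help decide whether it is studied further. Uncommon severe events matter in that setting, and they are seen and bounded better in 70 patients than in 35. The plan gives neither a pooled estimate nor its precision.

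**Working it through.** **Inputs.** 35 patients per cohort, 70 in all (Section 8.1). Stated precision: 17 points at n = 35 (Section 8.1). If the run-in triggers the other schedule, 70 − 6 = 64 patients start on the phase II regimen (Section 2.1.1). The documents give no number of enrolled but undosed patients, so this is an assumption, called u. The true toxicity rate of 30% is also an assumption, for illustration.

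**Step 1: reproduce the plan's figure.** The normal-approximation half-width is largest at a rate of 50%: 1.96 × √(0.25/n). At n = 35 this is 1.96 × √(0.25/35) = 0.166. Half the width of the widest exact (Clopper-Pearson) interval is 0.173. Both round to the stated 17 points.

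**Step 2: the same formulas with pooled patients, plus two measures for uncommon events.** The upper limit with no events is the two-sided exact 95% limit, 1 − 0.025^(1/n). The chance of seeing at least one case of a toxicity with true rate p is 1 − (1 − p)^n.

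| | n = 35 | n = 64 | n = 70 |
|---|---|---|---|
| Half-width, normal approximation (points) | 16.6 | 12.3 | 11.7 |
| Half-width, exact (points) | 17.3 | 12.8 | 12.2 |
| Upper 95% limit with no events | 10.0% | 5.6% | 5.1% |
| Chance of at least one case, p = 3% | 66% | 86% | 88% |
| Chance of at least one case, p = 2% | 51% | 73% | 76% |

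**Step 3: effect of undosed patients.** The observed rate is the true rate × (N − u)/N. With a true rate of 30%:

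| u | N = 35 | N = 70 |
|---|---|---|
| 0 | 30.0% | 30.0% |
| 1 | 30 × 34/35 = 29.1% | 30 × 69/70 = 29.6% |
| 3 | 30 × 32/35 = 27.4% | 30 × 67/70 = 28.7% |
| 7 | 30 × 28/35 = 24.0% | 30 × 63/70 = 27.0% |

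Each undosed patient costs 30/35 = 0.9 points in one cohort, or 30/70 = 0.4 points in the pooled set. In relative terms the loss is u/N: 2.9% per undosed patient in 35, and 1.4% in 70.

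**The case against.** The strongest reply is that this is a matter of wording and not a demonstrated bias. Section 5.4 intends all enrolled patients to receive the combination, and a screening number is assigned at consent (Section 7.1.1.6), so a consented patient need not be an enrolled one. If enrolment means starting treatment, the two sets coincide. The only safety rate that drives a decision, the run-in DLT rate, is already protected by the replacement rule in Section 5.9. The other toxicity tables are descriptive, and no threshold is set that a shift of one point could cross. This stands, and it limits the weight of the first issue. It does not remove it: *enrolled* is not defined, and the protection in Section 5.9 covers the DLT rate only.

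On pooling, the cohorts are different diseases with different treatment backgrounds, so toxicity by cohort is a legitimate display. That also stands, and is why the by-cohort table should remain.

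A reader might infer more than the text supports, in four ways:

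- That toxicity rates *are* diluted. This depends on undosed patients, and the documents report none.
- That no event before the first dose can be recorded. Serious events are reported from consent.
- That half the safety information goes unused. Two cohort tables use all 70 patients, and neither Section 3.1 nor Section 8.2 excludes an overall table.
- That 17 points is the planned precision for safety. The sentence speaks of frequencies in general.

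**Conclusion.** The point holds in a limited form. Section 8.1 sets an all-enrolled denominator for the primary safety endpoint, which does not match the start of general adverse event recording in Section 7.2. The resulting error is zero if every enrolled patient is dosed. Otherwise it is small and always in the favourable direction: about 0.9 points per undosed patient in 35, at an assumed true rate of 30%.

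Separately, safety is described by cohort and precision is given only for 35 patients, while the objective, the combination and the run-in decision are common to both cohorts. A stated pooled estimate would bring the half-width from about 17 to about 12 points, and would roughly halve the upper limit for a toxicity not seen at all (10.0% to 5.1%). The figures for 70 assume that the run-in leaves the regimen unchanged and that all 70 are treated. If the regimen changes, the pool on the phase II regimen is 64 and the half-width is 12 to 13 points. No decision rule in the plan changes either way.

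**What to change.** In Sections 8.1 and 8.2:

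1. Define the safety set as all patients who received at least one dose of either drug. Keep all enrolled patients for efficacy, and say at what step a patient counts as enrolled.
2. Report toxicity pooled over treated patients on the same regimen, with exact 95% confidence intervals, and also by cohort. If the run-in leads to a change of schedule, show the six run-in patients separately from the expansion patients.
3. State the precision of each: about ±12 points for 70 patients, about ±12 to 13 for 64, and ±17 for 35.

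The cost is a few lines of text and one extra table. The sample size, the response test and data collection stay as they are. The drawback is that a pooled rate can hide a difference between the cohorts, which the by-cohort table would show.

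### Does the 11-of-35 success rule contradict the exact one-sided 0.07 level stated for it?

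*Combined protocol and SAP*

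**What the plan says.** Section 8.1 gives one design statement, used for both cohorts. It plans to "enroll 35 patients in Cohort 1 and 35 patients in Cohort 2", and the run-in patients count: "All patients enrolled in the study (both in the phase I run in and phase II expansion) will be analyzed". The test is described as "using a 1-sided 0.07 level (exact) test with a null hypothesis of 20% response rate", against "an alternative of 40%, and 89% power (exact"). The decision threshold is named directly: "11/35 (31%) responses would be considered evidence to rule out an RR of < 20"%. A separate sentence on precision follows: "With 35 patients, frequencies can be estimated to within 17% with 95% confidence".

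Response is a secondary objective (Section 3.2); safety and tolerability are primary (Sections 3.1 and 4.2.3). Section 8.1 does not say whether 0.07 is a ceiling that the test must not exceed or the attained size of the 11-of-35 rule printed to two decimals.

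**The concern.** By the usual textbook definition, a level is an upper bound on the type I error. Someone who takes 0.07 as that bound and computes the exact tail for 11 of 35 at a 20% rate gets 0.0747, which exceeds it. The smallest threshold with exact size at or below 0.0700 is 12, where power falls to 80.5%. The stated 89% power would then belong to a different test from the one named.

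If that were right, the two halves of the sentence would disagree at exactly 11 responses: the threshold would declare success while the test at its own level would not reject. That outcome has probability 0.0747 − 0.0344 = 4.0% at a true rate of 20% and 0.8877 − 0.8048 = 8.3% at 40%, in each cohort. Section 4.1.2 says that response rates, with safety, will inform whether the combination is studied further, so a contradiction there would matter.

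**Working it through.** **Inputs, all from Section 8.1:** n = 35 per cohort, single stage; null rate p0 = 0.20; alternative p1 = 0.40; success if X ≥ 11; stated level 0.07 (two decimals); stated power 89% (whole percent). Both are labelled exact.

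**Formula.** For threshold r,

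P(X ≥ r | n, p) = Σ (k = r to n) C(n, k) p^k (1 − p)^(n − k).

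Size uses p = 0.20 and power uses p = 0.40.

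**Step 1: the plan's own rule.**
- Size: P(X ≥ 11 | 35, 0.20) = 0.0747, which prints as 0.07.
- Power: P(X ≥ 11 | 35, 0.40) = 0.8877, which prints as 89%.
- Threshold: 11/35 = 0.3143, which prints as 31%, as stated.

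**Step 2: could the printed pair belong to another rule?**

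| Rule | Exact size at 20% | Exact power at 40% |
|---|---|---|
| ≥10 of 35 | 0.1457 | 0.9425 |
| **≥11 of 35** | **0.0747** | **0.8877** |
| ≥12 of 35 | 0.0344 | 0.8048 |
| ≥11 of 34 | 0.0620 | 0.8617 |
| ≥11 of 36 | 0.0889 | 0.9096 |

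Only 11 of 35 gives 0.07 with 89%. Level, power, sample size and threshold therefore fit together as one design. The 12-of-35 rule would have been printed as 0.03 and 80%.

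**Step 3: the lower confidence limit.** At 11 of 35 the exact one-sided 93% lower limit is 19.78%, just under 20%. With an error probability of 0.0747 instead of 0.0700, the limit is 20.00%. This is the comparison of 0.0747 with 0.0700 seen from the other side. It is not independent evidence.

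**Step 4: the 95% interval.** The exact two-sided 95% interval at 11 of 35 is 16.9% to 49.3% and includes 20%. That interval corresponds to a one-sided test at 2.5%, which the plan does not use for its rule. The plan's 95% sentence concerns precision: 1.96 × √(0.25/35) = 0.166, which prints as 17%.

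**Step 5: was a normal approximation used?** With continuity correction the normal tail is 0.0696; without it, 0.0455. Since 0.0696 and 0.0747 both print as 0.07, the printed figure cannot show that an approximation was used. The plan says exact, and the exact calculation agrees with it.

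**Step 6: two cohorts.** If both true rates are 20%, and taking the cohorts as independent, the chance of at least one false claim is 1 − (1 − 0.0747)² = 14.4%. With 0.0700 it would be 1 − 0.93² = 13.5%. Section 8.1 applies the test to each cohort on its own denominator of 35 and makes no family-wise claim, so this figure contradicts nothing in the plan.

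**The case for a change.** The strongest contrary case is literal. The plan calls 0.07 a level and labels it exact; it does not say the figure was rounded. Under the standard definition, an exact p-value of 0.0747 does not reject at 0.0700. Rounding an error rate downward understates it, and here the understatement falls at the one outcome where the decision turns. If a reader raised this after exactly 11 responses had been seen, choosing between level and threshold at that point would be post hoc.

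Part of this stands: 0.075 would be the more accurate figure to print, and a strict-ceiling reading is exceeded by 0.0747 − 0.0700 = 0.0047. The contradiction does not follow. Section 8.1 nowhere presents 0.07 as a cap. A nominal cap would usually be a conventional figure such as 0.05 or 0.10; 0.07, marked exact and paired with an equally specific 89%, looks like the attained operating characteristics of the chosen threshold. Nor is the decision at 11 left open, because the same sentence states in advance that 11 of 35 counts as evidence against the null.

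The stakes are also lower than they might seem. This is the only hypothesis test in Section 8, but not the only numerical decision rule in the protocol: Section 2.1.1 sets one on dose-limiting toxicities in the first six patients, which selects the phase II regimen. One sentence in Section 2.1.2 links response and progression-free survival to a primary endpoint, but the objectives in Sections 3.1 and 3.2 place response as secondary. Section 4.2.3.1 also brings in overall and progression-free survival when judging whether further study is justified.

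**Conclusion.** The concern does not hold. The rule of 11 or more responses in 35 has exact size 0.0747 and exact power 0.8877. These are the stated 0.07 and 89% at the precision Section 8.1 uses, and no other threshold at that sample size yields them. The 12-of-35 alternative with 80.5% power describes a design the plan does not propose.

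This rests on reading 0.07 as a rounded attained size, which the text permits and its figures support. If the sponsor had meant a strict ceiling of 0.0700, the rule would exceed it by 0.0047; nothing in the plan indicates that intention. An extra decimal in the printed level would leave the threshold, the sample size, the power and the inference at 11 responses as they are, so no change is required.
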